### **2.8.1.2 Adverse events of special interest / grouping of AEs**

The number and percentage of patients who reported treatment-emergent adverse events of special interest (AESI) will be summarized by risk name, PT, maximum severity (based on CTCAE grades) and treatment group.

In addition, the number and percentage of patients who reported treatment-emergent co-morbid AE known to occur with COVID-19 will be summarized by risk name, PT, maximum severity, and treatment group.

Risk names will be sorted alphabetically and, within each risk name, the PTs will be sorted in descending order of frequency in the ruxolitinib + SoC arm. If a patient reported more than one adverse event with the same PT, the AE will be counted only once. If a patient reported more than one AE within the same risk, the patient will be counted only once at that risk.

The Compound Case Retrieval Strategy (CRS) will be used to determine the MedDRA search criteria to be used to identify AESI and treatment-emergent co-morbid AE known to occur with COVID-19. The most recent list of AESI at the time of database lock will be used.

A listing for all AESI will be provided.

## **2.8.2 Deaths**

Fatal AEs will be summarized and listed as specified in [Section 2.8.1](#).

## **2.8.3 Laboratory data**

Summaries of laboratory data will include treatment-emergent measurements, which are defined as measurements taken post-baseline and up to the last study visit.

Grading of laboratory values will be assigned programmatically as per the Common Terminology Criteria for Adverse Events (CTCAE) Version 5.0. The calculation of CTCAE grades will be based on the observed laboratory values only; clinical assessments will not be taken into account.

CTCAE Grade 0 will be assigned for all non-missing values not graded as 1 or higher.

The following summaries will be produced for hematology and chemistry laboratory data (by laboratory parameter and treatment):

- Shift tables using CTCAE grades to compare baseline to the worst treatment-emergent value.

The baseline value is the last value prior to first dose of double-blind treatment.

All laboratory data will be listed, with CTCAE grades by treatment group, patient, and visit/time.

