5.2 Exclusion criteria

Participants meeting **any** of the following criteria are **not** eligible for inclusion in this study.

1. History of hypersensitivity to any drugs or metabolites of similar chemical classes as ruxolitinib.
2. Presence of severely impaired renal function defined by serum creatinine > 2 mg/dL (>176.8 $\mu\text{mol/L}$), or have estimated creatinine clearance < 30 ml/min measured or calculated by Cockcroft Gault equation or calculated by the updated bedside Schwartz equation.
3. Suspected uncontrolled, active bacterial, fungal, viral, or other infection (besides COVID-19).
4. Current or history of active TB infection.
5. History of progressive multifocal leukoencephalopathy (PML).
6. Currently intubated or intubated between screening and randomization.
7. In intensive care unit (ICU) at time of randomization.
8. Patients who are on anti-rejection, immunosuppressant or immunomodulatory drugs (i.e. tocilizumab, ruxolitinib, canakinumab, sarilumab, anakinra).
9. Intubated or in ICU for COVID-19 disease prior to screening.
10. Participating in any other investigational or interventional trials.
11. Unable to ingest tablets at randomization.
12. ALT ≥ 5 x ULN detected at screening (according to local laboratory reference ranges).
13. Patients who have evidence of liver cirrhosis (Child A to C).
14. ANC $< 1000/\mu\text{L}$ at screening.
15. Platelet count $< 50,000/\mu\text{L}$ at screening.
16. Pregnant or nursing (lactating) women.
17. Females ≥ 12 and < 18 years of age and of childbearing potential (e.g. are menstruating) who do not agree to abstinence or, if sexually active, do not agree to the use of highly effective contraception as defined below, throughout the study and for up to 30 days after stopping treatment,

OR

Females ≥ 18 years of age and of child-bearing potential, defined as all women physiologically capable of becoming pregnant, unless they are using highly effective methods of contraception as defined below, throughout the study and for up to 30 days after stopping treatment.

Highly effective contraception methods include:

- Total abstinence (when this is in line with the preferred and usual lifestyle of the patient). Periodic abstinence (e.g., calendar, ovulation, symptothermal, post-ovulation methods) and withdrawal are not acceptable methods of contraception.

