6.6.2 Recommended treatment of adverse events

Dose reductions or interruptions for patients that do not tolerate the dosing schedule and are attributed to study drug are permitted in order to allow the patient to continue on the study treatment. Adverse events will be assessed and graded according to the Common Terminology Criteria for Adverse Events (CTCAE) Version 5.0 as described in [Section 10.1.1](#).

Neutropenia (Growth factor supplementation and transfusion should be provided as clinically indicated.)

Grade 3 (ANC < 750 - 500/mm³): Reduce dose to one tablet per day, monitor ANC daily until resolved to ≤ Grade 2, then resume initial dose level.

Grade 4 (ANC < 500/mm³): Hold dose, monitor ANC daily until resolved to ≤ Grade 3, then resume with reduced dose of one tablet per day. If resolves to ≤ Grade 2, can resume initial dose level.

Thrombocytopenia (transfusion support should be provided as clinically indicated)

For platelet counts < 20,000/mm³: Hold dose until resolved to > 35,000/mm³, then resume at a reduced dose level of one tablet per day. If counts are stable, dose may be cautiously re-escalated.

Dose reductions or interruptions for non-hematologic toxicity are permitted in order to allow the patient to continue on the study treatment. Dose adjustments for different ranges of non-hematologic toxicity are described below. The objective of the dose adjustment rules is to optimize treatment response for each individual patient while avoiding significant non-hematologic toxicities.

AST/ALT elevation

See [Appendix 1](#) for stopping or interrupting study drug for elevated ALT/AST.

Other adverse events (non-hematological) attributed to study drug

Recommendation for Grade 1 or 2: Maintain dose level.

Grade 3: Hold dose until resolved to baseline or Grade 1.

Grade 4: Discontinue from study treatment.

Medication used to treat adverse events (AEs) must be recorded on the appropriate eCRF.

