8.4.1 Laboratory evaluations

Laboratory evaluations will be performed by a local laboratory. Results from tests or examinations done as part of routine care may be used as specified in the table of assessments (See [Table 8-1](#)).

[figure not shown]
Hematology

Hemoglobin, hematocrit, red blood cell count, white blood cell count with differential, and platelet count will be measured according to the assessment schedule in [Table 8-1](#).

Chemistry

BUN/urea, creatinine, creatine kinase, total bilirubin, AST, ALT, alkaline phosphatase, sodium, potassium, chloride, calcium, bicarbonate, total protein, albumin, and glucose will be measured according to the assessment schedule in [Table 8-1](#). If a given test is not available locally, this should be documented on the eCRF.

If the total bilirubin concentration is increased above 1.5 times the upper limit of normal range, the total bilirubin will be differentiated into the direct and indirect reacting bilirubin.

Sample(s) will be collected at the time point(s) defined in the Assessment Schedule ([Table 8-1](#)). If a given test is not available locally, this should be documented on the eCRF.

Drug-induced liver injury monitoring

For patients with elevated liver tests, additional laboratory tests as denoted in [Appendix 1](#) ([Table 16-1](#), [Table 16-2](#) and [Table 16-3](#)) should be obtained as specified.

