12.5.2.3 Clinical laboratory evaluations

All laboratory data will be listed by treatment group, participant, and visit/time and if normal ranges are available abnormalities will be flagged. Summary statistics will be provided by treatment and visit/time.

[REDACTED]

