16.1 Appendix 1: Liver event and laboratory trigger definitions & follow-up requirements

Table 16-1 Liver event and laboratory trigger definitions

	Definition/ threshold
Liver laboratory triggers	
 ALT or AST > 5 × ULN
If ALT, AST and total bilirubin normal at baseline:	
 ALP > 2 × ULN (in the absence of known bone pathology) Total bilirubin > 3 × ULN (in the absence of known Gilbert syndrome) ALT or AST > 3 × ULN and INR > 1.5 Potential Hy's Law cases (defined as ALT or AST > 3 × ULN and Total bilirubin > 2 × ULN [mainly conjugated fraction] without notable increase in ALP to > 2 × ULN) Any clinical event of jaundice (or equivalent term) ALT or AST > 3 × ULN accompanied by (general) malaise, fatigue, abdominal pain, nausea, or vomiting, or rash with eosinophilia Any adverse event potentially indicative of a liver toxicity*
If ALT or AST abnormal at baseline:	
 ALT or AST > 2x baseline or > 300 U/L (whichever occurs first)

*These events cover the following: hepatic failure, fibrosis and cirrhosis, and other liver damage-related conditions; non-infectious hepatitis; benign, malignant and unspecified liver neoplasms ULN: upper limit of normal

Table 16-2 Follow up requirements for liver laboratory triggers with liver symptoms

	ALT	TBL	Liver Symptoms	Action
ALT increase without bilirubin increase:				
	If normal at baseline: ALT > 3 x ULN If elevated at baseline: ALT > 2 x baseline or > 300 U/L (whichever occurs first)	Normal For patients with Gilbert's syndrome: No change in baseline TBL	None	
 • No change to study treatment • Measure ALT, AST, ALP, GGT, TBIL, INR, albumin, CK, and GLDH (if available at local laboratory) in 48-72 hours. • Follow-up for symptoms.
	If normal at baseline: ALT > 5 x ULN for more than two weeks If elevated at baseline: ALT > 3 x baseline and > 10x ULN	Normal For patients with Gilbert's syndrome: No change in baseline TBL	None	
	If normal at baseline: ALT > 8 x ULN	Normal	None	
ALT increase with bilirubin increase:				

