### **5.3 Laboratory parameters derivations**

Grade categorization of lab values will be assigned programmatically as per Common Terminology Criteria for Adverse Events (CTCAE) version 5.0.

A severity grade of 0 will be assigned for all non-missing lab values not graded as 1 or higher. CTCAE Grade 5 is not defined for laboratory values.

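### The SAP's Grade 0 rule does not separate laboratory values checked and found below Grade 1 from values that could not be graded because a reference limit is missing

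*SAP*

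**What the plan says.** SAP 2.8.3 has grades assigned by program under CTCAE version 5.0 and adds: "The calculation of CTCAE grades will be based on the observed laboratory values only; clinical assessments will not be taken into account". It then sets the default: "CTCAE Grade 0 will be assigned for all non-missing values not graded as 1 or higher". SAP 5.3 says the same: "A severity grade of 0 will be assigned for all non-missing lab values not graded as 1 or higher". The only laboratory summary named in SAP 2.8.3 is a shift table from the baseline grade to the worst treatment-emergent grade. All results are also listed with their grades.

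On the source of the data, Protocol 8.4.1 states: "Laboratory evaluations will be performed by a local laboratory". The footnotes to Protocol Table 8-1 allow routine-care results to be used, including results from up to 48 hours before the screening visit as screening values. On listings, Protocol 12.5.2.3 says that "if normal ranges are available abnormalities will be flagged".

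**The concern.** The qualifier in the rule attaches to the laboratory value, not to its reference limit. A result that is in the database without the upper or lower limit needed to grade it is non-missing and has not been graded 1 or higher, so it falls into Grade 0 by default. The program has no other category, and clinical judgement is excluded from grading.

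Two errors can follow in the shift table. If the on-study values cannot be graded, an abnormality is hidden; a patient with a gradable Grade 2 baseline could even appear to improve to Grade 0. If the baseline cannot be graded, it appears as Grade 0, and a later gradable value can look like a new worsening.

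Laboratory changes are part of the secondary safety endpoint (Protocol Table 2-1, SAP Table 1-1). The SAP handles comparable gaps differently elsewhere. An adverse event with no CTCAE grade is counted in the all-grades column (SAP 2.8.1), missing categorical baseline data get a category of their own (SAP 2.3.2), and doubt about adverse-event timing is resolved towards treatment-emergent (SAP 5.1.2).

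**Working it through.** The plan gives no figure to reproduce here. The check applies the rule literally, asks whether its trigger is foreseeable, and then illustrates the size under stated assumptions.

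**Step 1: the rule applied to four cases.**

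| Value in database | Result of grading | Grade shown |
|---|---|---|
| present | Grade 3 | 3 |
| present | checked, below Grade 1 | 0 |
| present | not possible, limit missing | 0 |
| missing | none | none |

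The second and third rows give the same output.

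**Step 2: is the third row foreseeable?** Laboratories are local, routine-care results are accepted, and Protocol 12.5.2.3 makes flagging conditional on ranges being available. Criteria that need a limit are present in the documents. Protocol Table 16-1 has a liver trigger of "ALT or AST > 5 × ULN", and Table 16-3 pairs bilirubin bands in ULN multiples with follow-up to Grade 1 or lower. By contrast, the neutropenia rule in Protocol 6.6.2, "Grade 3 (ANC < 750 - 500" per mm³, uses an absolute count and needs no limit. The documents do not reproduce the CTCAE laboratory criteria, so it is an assumption that a given parameter is range-dependent.

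**Step 3: illustration for one range-dependent parameter.** Let p be the true share of patients whose worst grade is 1 or higher, and m the share with no usable limit. Neither is in the documents. Assume that m is unrelated to abnormality and equal in both arms, and that affected patients have no on-study value gradable at 1 or higher. Then:

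share shown = p × (1 − m)

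- p = 30%, m = 2%: 0.30 × 0.98 = 29.4%
- p = 30%, m = 5%: 0.30 × 0.95 = 28.5%
- p = 30%, m = 10%: 0.30 × 0.90 = 27.0%
- p = 30%, m = 20%: 0.30 × 0.80 = 24.0%

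Patients hidden = n × p × m, with the planned 268 and 134 patients per arm (SAP 1.1):

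- p = 30%, m = 5%: 268 × 0.30 × 0.05 = 4.0 on ruxolitinib; 134 × 0.30 × 0.05 = 2.0 on placebo
- lowest, p = 10%, m = 2%: 268 × 0.10 × 0.02 = 0.5; 134 × 0.10 × 0.02 = 0.3
- highest, p = 50%, m = 20%: 268 × 0.50 × 0.20 = 26.8; 134 × 0.50 × 0.20 = 13.4

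The arm difference shrinks by the same factor. With assumed true shares of 30% and 20%, the table shows 28.5% and 19% at m = 5% (9.5 points), 27% and 18% at m = 10% (9 points), and 24% and 16% at m = 20% (8 points), against a true 10 points. For a parameter graded on absolute counts alone, the effect is zero.

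**The case against.** The strongest reply is that the liver-test limits must exist at the sites. Exclusion criterion 12 on ALT applies to values "detected at screening (according to local laboratory reference ranges"), Protocol 8.4.1 requires bilirubin to be fractionated above a multiple of the upper limit, and Protocol Tables 16-1 to 16-3 need the ULN during treatment. A site without an ALT range could not run the protocol. The conditional wording in Protocol 12.5.2.3 has a near-twin for vital signs in 12.5.2.2, so it may be generic. This stands. It narrows the realistic case to a limit known at the site but not captured in the database. Protocol 11.2 provides for queries on missing values, but the documents do not say that every limit will be obtained.

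It is also fair that the shift table uses the worst of many results: in hospital, laboratory tests fall on alternate days, plus Days 15 and 29. One ungradable result changes nothing if another carries the worst grade. The error needs ungradable values throughout, at the abnormal time, or at baseline.

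Other outputs limit the harm. A high value can be seen beside its Grade 0 in the listing. Protocol 12.5.2.3 plans summary statistics by visit, and SAP section 4 does not withdraw them. Abnormalities that are clinically significant, cause symptoms or need therapy are reported as adverse events (Protocol 10.1.1). These are real safeguards, but none corrects the grade in the shift table.

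A reader might infer that the SAP has decided to report abnormal values as normal. The documents do not support that: neither section calls Grade 0 normal, and neither mentions missing limits. The misclassification is a consequence of the rule's wording, not a stated intention.

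**Conclusion.** The point holds as a defect in a stated rule. SAP 2.8.3 and 5.3 merge two different situations into Grade 0, and for range-dependent parameters the shift table can be wrong in either direction: toxicity hidden on study, or a false Grade 0 baseline.

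Its size is unknown. The illustrated figures rest wholly on assumed values of p and m and on the independence assumptions given with them. They show how the effect scales and do not estimate it. A reader might take them as evidence that toxicity will be materially understated, or that whole sites will show only Grade 0 to Grade 0. With no stated frequency of missing limits, and with protocol rules that require sites to hold liver-test ranges, neither inference is supported.

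The effect is confined to descriptive safety reporting; the primary analysis, the significance level and power are untouched. The change is still worth making, because under the present rule the shift tables cannot reveal how often limits were missing.

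**What to change.** In SAP 2.8.3 and 5.3, replace the default with a rule such as: *Grade 0 is assigned only when the value and the reference limit needed for grading are both available and no criterion for Grade 1 or higher is met; otherwise a non-missing value that has not received Grade 1 or higher is classified as not gradable.* Show 'not gradable' as a separate row and column in the shift tables, with counts by arm.

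I would not go on to substitute a standard range for a missing local one. That is a separate and debatable choice, since it can misgrade values itself.

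The cost is one sentence in each section and one extra category in the tables. Some patients will move out of Grade 0. If all limits turn out to be present, the category is empty and nothing is lost.

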6.1.4 Treatment duration

The planned duration of treatment is 14 days. An additional 14 days of study drug may be given, if in the opinion of the investigator, the patient's clinical signs and symptoms are not improved or worsen and the potential benefit outweighs the potential risk. Participants may be discontinued from treatment earlier due to unacceptable toxicity, disease progression and/or treatment is discontinued at the discretion of the investigator or the participant. Treatment will not be provided upon completion of the study.

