When possible, the sequence of assessments at each visit should be as follows (at visits required in the schedule of assessments).

- Efficacy assessments: clinical status, clinical signs and symptoms, oxygen saturation, consciousness, ventilatory status;
- Safety assessments: vital signs, review of adverse events, concomitant medications;

Laboratory samples: on days indicated in schedule of assessments.

Results from tests or examinations done as part of routine care prior to the screening visit may be used for the study as indicated in [Table 8-1](#) (Assessment Schedule). **However, the above-mentioned efficacy assessments (clinical status, clinical signs and symptoms, oxygen saturation, consciousness, ventilatory status) must be done in the morning of randomization between 7 AM and 12 PM, prior to administering study drug.**

If a patient is discharged from the hospital during the study period, the Clinical Status Evaluation with 9-point ordinal scale will be performed via telephone call (between 7 AM and 12 PM local time) daily except for Day 15 and Day 29 when it will be performed in clinic. For Day 15 and Day 29, if an in-clinic visit is not possible, the visit may be performed in an appropriate setting, including at home, with appropriate study personnel.

Table 8-1 Assessment Schedule

All assessments will be obtained while patient is in hospital. Once patient is discharged, assessments will be done via the telephone as indicated in the table below with the exception of Day 15 and Day 29 which require in-clinic assessments. For Day 15 and Day 29, if an in-clinic visit is not possible, the visit may be performed in an appropriate setting, including at home, with appropriate study personnel.

Study Day	Screening	Study Period				
	Screening	Day 1 (Randomization)	Day 2-14 (every day unless otherwise specified below)	Day 15	Day 16-28 (every day unless otherwise specified below)	Day 29 (End of study)
Informed consent (and assent if applicable) ¹	x					
Inclusion / Exclusion criteria	x	x				
Demographics / medical history (including co-morbidities checklist)	x					
SARS-CoV-2 virus confirmation ²	s					
Vital signs ³ (between 7 AM and 12 PM local time)	x ⁴	x	x (while in hospital)	x	x (while in hospital)	x
SpO ₂ assessment (between 7 AM and 12 PM local time – done at same time as vital signs)	x ⁴	x	x (while in hospital)	x	x (while in hospital)	x

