SpO ₂ assessment on room air (for patients on oxygen by nasal cannula (≤ 2L/min) (based on investigator medical judgement) (between 7 AM and 12 PM local time – done at same time as vital signs)			(only on day of discharge)	x	(only on day of discharge)	x
FiO ₂ assessment (between 7 AM and 12 PM local time – done at same time as vital signs)	x ⁴	x	x (while in hospital)	x	x (while in hospital)	x

Study Day	Screening	Study Period				
	Screening	Day 1 (Randomization)	Day 2-14 (every day unless otherwise specified below)	Day 15	Day 16-28 (every day unless otherwise specified below)	Day 29 (End of study)
Consciousness assessment (between 7 AM and 12 PM local time – done at same time as vital signs)		x	x (while in hospital)	x	x (while in hospital)	x
Clinical Status Evaluation with 9-point ordinal scale (if patient is discharged to home, telephone call daily except for Day 15 and Day 29 when in clinic) (between 7 AM and 12 PM local time)		x	x (via telephone if not in hospital)	x	x (via telephone if not in hospital)	x
Height (measured or patient or guardian/health proxy reported), weight, BMI	x ⁴					x
Physical exam	s ⁴					
Ventilatory status (e.g. mechanical ventilation, supplemental oxygen, intubation and non-invasive ventilation [e.g. CPAP, BIPAP, etc.]	x ⁴	x	x (via telephone if not in hospital)	x	x (via telephone if not in hospital)	x
Drug dispensation and administration		x	Days 2-14	x (if applicable)	Days 16-28 (if applicable)	x (if applicable)
Assessment of re-treatment (if second course of 14 day treatment is needed)				s		
Reconcile study medication				s		s
Collect unused study medication				s		s
Hematology ⁵ (local labs)	x ⁶	x ⁷	Days 3, 5, 7, 9, 11, 13 (while in hospital)	x	Days 17, 19, 21, 23, 25, 27 (while in hospital)	x
Clinical chemistry, [REDACTED] [REDACTED] ⁵	x ⁶	x ⁷	Days 3, 5, 7, 9, 11, 13 (while in hospital)	x	Days 17, 19, 21, 23, 25, 27 (while in hospital)	x

Study Day	Screening	Study Period				
	Screening	Day 1 (Randomization)	Day 2-14 (every day unless otherwise specified below)	Day 15	Day 16-28 (every day unless otherwise specified below)	Day 29 (End of study)
Serum pregnancy test (local labs); results must be reviewed prior to randomization	x ⁸					x
Chest x-ray (CXR) or chest CT scan ⁹	x					
ECG (local) ⁴	s					
Adverse events	x	x	x (via telephone if not in hospital)	x	x (via telephone if not in hospital)	x

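### If hospital stay differs between arms, the SAP's single worst-value laboratory table will tend to show fewer short-lived abnormalities in the shorter-stay arm

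*SAP*

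**What the plan says.** **Testing.** In protocol Table 8-1 the hematology and chemistry rows read "Days 3, 5, 7, 9, 11, 13 (while in hospital" for the first fortnight and "Days 17, 19, 21, 23, 25, 27 (while in hospital" for the second. Assessments after discharge are by telephone, "with the exception of Day 15 and Day 29 which require in-clinic assessments", and the laboratory rows are marked on both those days without a hospital condition.

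**Dosing.** Protocol 6.1.4: "The planned duration of treatment is 14 days". It continues: "An additional 14 days of study drug may be given, if in the opinion of the investigator" judges that this is warranted. In Table 8-1 the row "Drug dispensation and administration" lists Days 2-14 with no in-hospital restriction, unlike the laboratory rows.

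**Reporting.** For laboratory data, protocol 12.5.2.3 says: "Summary statistics will be provided by treatment and visit/time". SAP 2.8.3 lists "Shift tables using CTCAE grades to compare baseline to the worst treatment-emergent value" and a patient-level listing. In the visible text it gives no by-visit table and no count of tests. SAP Section 4, which records departures from the protocol, does not mention this. SAP Section 1, however, says the data will be analyzed according to Section 12 of the protocol.

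**The concern.** A patient's worst value can only stay the same or get worse as tests are added. Here the number of tests is set by length of stay, which is determined after randomization and analyzed as an efficacy endpoint (SAP 2.7.1.3). A patient discharged early can be taking study drug at home with no scheduled blood test until Day 15. An abnormality that begins after the last in-hospital test and resolves before Day 15 goes unseen, whereas the same abnormality in a patient still in hospital is recorded.

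If stays differ between arms, the worst-value table therefore mixes a difference in safety with a difference in how closely patients were observed. Protocol 4.6 gives decreased hematopoietic proliferation as the primary risk. It describes the cytopenias seen with ruxolitinib as reversible and the transaminase rises as mild and reversible. Short-lived abnormalities are the ones this schedule can miss. Clinically significant laboratory change is also part of the stated safety objective.

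**Working it through.** The documents give no figure on this point, so there is none to reproduce.

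**1. Scheduled tests (Table 8-1).** In hospital throughout: 6 (Days 3-13) + 1 (Day 15) + 6 (Days 17-27) + 1 (Day 29) = 14. Last hospital day 5: Days 3, 5, 15 and 29 = 4. Last hospital day 9: 4 + 2 = 6.

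**2. Detection for one patient.** Assumptions not in the documents: onset is uniform over Days 1-15; the abnormality lasts L days, with L at least 3; it counts if any scheduled test falls while it is present. Let T be the last alternate-day test in hospital by Day 13 (T = 1 if there is none). Onsets from Day 1 to T are caught in hospital, because tests are two days apart. Onsets in the L days before Day 15 are caught on Day 15. So

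P(detect) = min{1, (T − 1 + L)/14}.

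For L = 5:
- last hospital day 3: 7/14 = 0.50
- day 5: 9/14 = 0.64
- day 7: 11/14 = 0.79
- day 9: 13/14 = 0.93
- day 12 (T = 11): 15/14, capped at 1.00

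For L = 14 it is 1.00 whatever the stay, because Day 15 catches every case.

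**3. Detection for an arm.** The only stay figure in the documents is a median of 12 days (protocol 4.3, from a cited trial). I take stay as log-normal with log SD 0.6 (assumed), median m = 12 in one arm and shorter in the other. The chance of still being in hospital on test day t is S(t) = Φ[(ln m − ln(t − 1))/0.6]. For t = 3, 5, 7, 9, 11, 13:
- m = 12: 0.999, 0.966, 0.876, 0.750, 0.619, 0.500
- m = 8: 0.990, 0.876, 0.684, 0.500, 0.355, 0.250

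For L = 3, step 2 gives: detection = 3/14 + (2/14)·[S(3)+S(5)+S(7)+S(9)+S(11)] + (1/14)·S(13).
- m = 12: 0.214 + (2/14)(4.210) + 0.036 = 0.851
- m = 8: 0.214 + (2/14)(3.405) + 0.018 = 0.719
- Ratio: 0.719/0.851 = 0.84

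Simulation under the same assumptions agrees with this formula. Apparent ratios, with equal true rates and every patient attending Days 15 and 29:

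| Abnormality lasts | 11 vs 12 days | 10 vs 12 | 8 vs 12 | 6 vs 12 |
|---|---|---|---|---|
| 3 days | 0.97 | 0.94 | 0.84 | 0.72 |
| 5 days | 0.98 | 0.96 | 0.89 | 0.80 |
| 7 days | 0.99 | 0.98 | 0.94 | 0.88 |
| 14 days | 1.00 | 1.00 | 1.00 | 1.00 |

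With equal stays the ratio is 1.00. Mean scheduled tests per patient are about 7.9, 6.0 and 5.0 at medians of 12, 8 and 6 days.

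**4. Attendance.** If 80% of discharged patients attend Days 15 and 29, the 8 vs 12 ratios become 0.83, 0.87, 0.91 and 0.96.

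**5. Fixed days only.** A summary limited to Days 15 and 29 gives about 1.00 at full attendance and about 0.95 at 80% (8 vs 12 days). The 0.95 counts non-attenders as having no abnormality, so the number tested has to be shown.

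**The case against.** - **The bias is conditional.** It needs unequal stays, and the documents do not say that stays will differ. A reader might infer that the plan makes ruxolitinib look safer. The documents do not support that: the direction depends on which arm goes home sooner, and a true drug effect could outweigh the artefact.
- **Day 15 limits the damage.** It falls just after the planned course and is due in everyone, so abnormalities that persist to then are caught in either arm. This stands, and it confines the point to short-lived abnormalities.
- **A larger size is tempting.** Treating tests as independent with a 3% chance each gives 1 − 0.97^6 = 16.7% against 1 − 0.97^8 = 21.6%, a ratio of 0.77. Values two days apart in one patient are not independent. Allowing for persistence, the same contrast in number of tests gives 0.84 to 1.00.
- **The by-visit summaries may not have been dropped.** SAP Section 1 defers to protocol Section 12, and SAP Section 4 lists no change to them. Protocol 12.5.2, in turn, leaves full details to the SAP. This is an inconsistency to resolve rather than a proven removal.
- **Other outputs exist.** Laboratory data are listed by patient, and cytopenias are summarized as adverse events of special interest. Telephone follow-up, however, cannot find an asymptomatic cytopenia that nobody measured. Repeat testing under protocol 6.6.2 and Appendix 1 starts only once an abnormality has been found. Routine-care results may be used, but they arise mostly in hospital and probably widen the gap.
- **Vital signs.** A reader might extend the point to SAP 2.8.4.2, but that section already summarizes by visit. Only its minimum and maximum share the dependence.

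**Conclusion.** The point holds as a conditional one. The only laboratory tabulation named in SAP 2.8.3 is sensitive to length of stay, and the fixed-day summaries that would be much less so appear in protocol 12.5.2.3 but not in SAP 2.8.3. The effect is nil with equal stays, small (0.94 to 1.00) for a difference of one or two days, and about 0.84 to 1.00 for medians of 8 against 12 days, depending on how long the abnormality lasts. These ratios rest on assumed onset, duration, stay distribution and full attendance, and the calculation ignores deaths. The tables are descriptive with no planned test, and the primary analysis is untouched. The change is still worth making because it concerns the drug's known toxicities and settles an undeclared difference between the two documents.

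**What to change.** In SAP 2.8.3:
1. State the by-visit laboratory summaries of protocol 12.5.2.3 explicitly.
2. Add CTCAE shift tables by arm from baseline to Day 15 and from baseline to Day 29, with the number tested in each arm.
3. Read between-arm differences mainly from Day 15. For patients whose treatment is not extended, Day 29 is about two weeks after dosing and says little about reversible effects.
4. Keep the worst-value table and show the number of tests per patient by arm beside it.

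For vital signs, at most add a count of measurements beside the minimum and maximum in SAP 2.8.4.2.

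The cost is SAP wording, two table shells and a count column, all from data already collected. No change to testing or dosing is proposed. The downside is that fixed-day tables miss abnormalities that come and go between visits, which is why the worst-value table stays. They also depend on survival and attendance, which is why the number tested must accompany them.
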